5.2 Phase 2 Study

At the completion of the phase 1b study, the safety of the PAC-1 and entrectinib combination will be assessed and recommendations will be provided regarding whether to proceed to the phase 2 portion of the study. The sponsor-investigator, Vanquish Oncology, and Genentech will review the DSMB recommendations, and make a decision regarding whether this combination is safe to warrant further study of this combination in a phase 2 study.

The primary objective of the Phase II trial is to determine the activity of the combination of PAC-1 and entrectinib for subjects with uveal melanoma as assessed by PFS at 3 months. Entrectinib, 600 mg orally, will be given Days 1 to Day 28 of each cycle and the recommended phase 2 dose (RP2D) of PAC-1 (PO) will be given on Days 1 to Day 21. Each cycle is 28 days. Treatment will continue until disease progression (based on RECIST 1.1 criteria), unacceptable toxicity, subject withdrawal of informed consent, or subject death either from progression of disease, the therapy itself, or from other causes. Subjects who voluntarily withdrew from study treatment, have progressive disease, or unacceptable toxicities will be followed for survival every 2 months for 12 months from start of study treatment, then every 3 months for up to 24 months.

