5.3 Administration of Study Drugs

Criteria for the initiation of a new cycle of treatment can be found in Section 6.1. All tablets are to be ingested as dispensed by research team (e.g. tablets may not be broken or crushed by subject); patients who have difficulty swallowing tablets will be excluded from the study. If vomiting occurs during the course of treatment, no re-dosing of the patient is allowed before the next scheduled dose. Missed doses will not be made up. A window of \pm 3 days may be applied to all study visits to accommodate observed holidays, inclement weather, scheduling conflicts etc. Date and time of each drug administration should be clearly documented in subject's chart and electronic case report forms (eCRFs).

Patients will keep a drug diary to record each dose of the study drugs and time of day when administered, and any side effects they are experiencing. Research staff will record information from the diaries, discuss any concerns the patient has regarding the treatment, and will also collect any unused medication during these visits. Patients will be closely monitored for toxicities and CTCAE v5 will be used to assess toxicities.

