6.1 Start of a New Cycle

A new treatment cycle will only be initiated when all of the following conditions are met:

- ANC $\geq 1,500/\text{mm}^3$
- platelets $\geq 100,000/\text{mm}^3$
- non-hematologic treatment related toxicities have improved to \leq Grade 1 or to the patient's baseline values (except alopecia)

If blood counts are below this threshold, blood work is to be repeated weekly until counts are at an acceptable level. Treatment will be restarted with appropriate dose modifications. If treatment is unable to restart within 4 weeks of the planned treatment date, the patient will be permanently discontinued from study therapy. **NOTE:** For Cycle 1 of the Phase 1b study only, the inability to restart therapy within 2 weeks of the planned date is a DLT (per section 5.1.2); however the patient is allowed an additional week of recovery and is allowed to remain on study if treatment restarts within 4 weeks.

For subjects who present to the clinic with toxicity during a current treatment cycle, the study drug may be stopped per the discretion of the site investigator if the toxicity is determined to be clinically significant.

Dosing interruptions are permitted in the case of medical / surgical events or logistical reasons not related to study therapy (e.g., elective surgery, unrelated medical events, patient subject vacation, and/or holidays). Subjects should be placed back on study therapy within 4 weeks of the scheduled interruption, unless otherwise discussed with the sponsor-investigator. The reason for interruption should be documented in the patient's subject's study record.

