6.2.1 PAC-1 Dose Reduction

Dose Reduction ^{a,b,c}	Dose	Dose
Starting Dose	750 mg daily	625 mg daily
First Dose Reduction	625 mg daily	500 mg daily
Second Dose Reduction	500 mg daily	375 mg daily
Third Dose Reduction	375 mg daily	250 mg daily
Fourth Dose Reduction	250 mg daily	NA

^a In the event a dose modification is needed, initiation of re-treatment should be delayed 1 to 2 weeks to allow for recovery from treatment-related toxicity

^b If the patient has not recovered after a 2-week delay, discontinue treatment

^c Up to four dose reductions are allowed if the starting dose is 750 mg. If subsequent cycles require additional dose reductions, treatment will be discontinued.

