4: A basic neurologic exam will be performed by the site investigator at screening, Day 1 of each Cycle of treatment and at the D30 safety follow up visit to monitor for neurologic toxicity. The Mini Mental Status Exam (MMSE) will be performed by a member of the research staff at screening and Day 1 of each Cycle of treatment to monitor for cognitive toxicity. The results of the MMSE and neurologic exam will be reviewed by the site investigator who will determine whether dose reduction of study drug(s) is required. This information should be retained.

5: CBC with differential and platelet to include: WBC, ANC, ALC, Hgb, PLT. Comprehensive metabolic profile (CMP) will be done at screening then Day 1 of each Cycle. During Cycle 1, a CMP should be performed at Cycle 1 Day 15. CMP to include glucose, calcium, BUN, creatinine, sodium, potassium, chloride, serum albumin, total bilirubin, alkaline phosphatase, AST, and ALT, ammonia, LDH and uric acid. Coagulation studies (PT/INR and PTT) will be done at screening then at the discretion of the treating investigator during treatment. For women of childbearing potential (WOCBP): urine or serum β hCG if clinically appropriate. If a urine test is done and it is positive or cannot be confirmed as negative, a serum pregnancy test will be required. Testing is required within 72 hours prior to initiation of study treatment. Urinalysis will be performed at screening.

6: Tumor response assessment will consist of evaluation by CT scans of chest and MRI or CT of abdomen and pelvis at screening and every odd numbered cycle starting after screening with CT scan before Cycle 3 (imaging selected for each subject should remain the same throughout the study); tumor imaging to be done at the safety follow up visit is at discretion of site investigator. If tumor assessments are available for subjects who have not yet experienced progressive disease (PD) at the time treatment is discontinued, the follow-up tumor evaluations will be documented in the eCRF until PD or death is confirmed, or until another treatment is initiated. MRI of the brain will be performed per standard of care for those subjects with a history of brain metastasis. A window of - 7 days may be used. CT/MRI images are to be submitted for central analysis. Images will be de-identified prior to sending to a central location. Central analysis to be performed upon receipt of funding.

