12. STATISTICAL CONSIDERATIONS

12.1 Study Design

This is a single arm study.

Phase 1b: The primary objective of the Phase Ib dose escalation cohort study is to establish the MTD of PAC-1 in combination with entrectinib in subjects with metastatic uveal melanoma. A standard “3+3” design will be used to establish the MTD. PAC-1 (PO) will be given daily on Days 1 through 21 of each cycle. Entrectinib (PO) will be given daily on Days 1 through 28 of each cycle. Each cycle will equal 28 days. Response will be evaluated after every 2 cycles. Treatment will continue until disease progression based on RECIST criteria or intolerable toxicity.

Phase 2: The primary objective of the Phase II trial is to estimate 3 months PFS using RECIST v1.1 in subjects with metastatic uveal melanoma treated with PAC-1 in combination with entrectinib. PAC-1 (PO) will be given daily on Days 1 through 21 of each cycle. Entrectinib (PO) will be given daily on Days 1 through 28 of each cycle. Each cycle will equal 28 days. Response will be evaluated after every 2 cycles. Treatment will continue until disease progression based on RECIST criteria or intolerable toxicity. Subjects who voluntarily stop the study, have progressive disease, or unacceptable toxicities will be followed for survival every 2 months for 12 months from start of study treatment, then every 3 months for up to 24 months.

Correlative research analyses include examining the relationship between procaspase 3 expression in archived tumor tissue to degree of clinical response.

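### Tumor scans follow cycle number but the primary endpoint is fixed at 3 months, so dose delays decide, in either direction, whether a progression is counted

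*Combined protocol and SAP*

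**What the plan says.** **Scan timing.** Section 7, footnote 6 places tumor imaging at screening and at "every odd numbered cycle starting after screening with CT scan before Cycle 3". Section 12.1 says "Response will be evaluated after every 2 cycles", and Section 5.1 and the synopsis agree. Section 5.2, the Phase 2 section, gives no scan schedule. No section dates on-treatment scans in weeks from treatment start. The imaging window runs one way only: "A window of - 7 days may be used".

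**Endpoint.** Section 2.4.2 defines the Phase 2 primary endpoint as the proportion alive without radiological progression at 3 months from treatment initiation. Section 9.9.3 runs PFS from treatment start to RECIST progression or death and censors at the last disease evaluation. Neither section has a rule for late or missed scans.

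**Delays.** Section 6.1 on toxicity: "If treatment is unable to restart within 4 weeks of the planned treatment date, the patient will be permanently discontinued from study therapy". Section 6.1 on interruptions unrelated to therapy: "Subjects should be placed back on study therapy within 4 weeks of the scheduled interruption", with exceptions possible after discussion with the sponsor-investigator. Section 6.4 ends therapy at a between-cycle delay of 4 weeks or more for a treatment-related event. Footnote b in Section 6.2.1 sets a shorter limit: "If the patient has not recovered after a 2-week delay, discontinue treatment". Section 6.3.2 repeats it for entrectinib. Section 5.3 adds "Missed doses will not be made up", so a hold within a cycle need not move the cycle count.

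**The concern.** The endpoint runs on calendar time and the scans run on cycle time. The two stay aligned only while every cycle starts on schedule. When a cycle slips, the scan slips with it, and only in the patients who are delayed. Whether a patient who has progressed is a failure or a success at 3 months then depends partly on how well the regimen was tolerated.

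This is one arm compared with a fixed 38%, so no control group shares the distortion. The sample size in Section 12.3 treats the 3-month status as a plain proportion, as if it were known for each patient at 3 months.

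**Working it through.** **1. The plan's own figure.** Inputs from Section 12.3: null 0.38, alternative 0.65, one-sided 0.05, 90% power, n = 32, and 35 after drop-off.
- Normal approximation: n = [(1.645 × √(0.38 × 0.62) + 1.282 × √(0.65 × 0.35)) / 0.27]² = 27.3, so 28. With continuity correction it is 30.9, so 31.
- Exact binomial at n = 32: reject at 18 or more, size 0.0275, power 0.888.
- Drop-off: 32 / 0.9 = 35.6, against 35 stated.

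The stated size is reproduced closely enough.

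**2. Day of the first scan.** From Section 5.2, "Each cycle is 28 days". Days are counted as elapsed since treatment start. Let d be the total delay accumulated at the starts of Cycles 2 and 3, and w the part of the -7-day window used (0 to 7).

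First scan = 28 + 28 + d − w = 56 + d − w. The undelayed second scan is at 112.

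The first scan misses the landmark when 56 + d − w exceeds 3 months:
- 3 months = 90 days: d > 34 with w = 0, or d > 41 with w = 7.
- 3 months = 91.3 days: d > 35, or d > 42 in whole days.

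**3. What the delay limits allow before Cycle 3 (two cycle starts, w = 0).**

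| Limit read | Largest d | First scan | Before the landmark? |
|---|---|---|---|
| 2 weeks (Sections 6.2.1, 6.3.2) | 2 × 14 = 28 | 84 | yes |
| 4 weeks (Section 6.1) | 2 × 28 = 56 | 112 | no |

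Under Section 6.4 each treatment-related delay must stay below 28 days, so the second row is then approached but not reached. Interruptions unrelated to therapy fall under Section 6.1 and could add to either row.

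**4. Effect on the recorded 3-month rate.** Assumptions: exponential PFS through the stated 3-month rate, progression seen only at scans, landmark L = 91.3 days, w = 0. If the first scan t is at or before L, the recorded rate is S(t) = S₃^(t/L). If it is later, no progression is recorded before L.

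| Total delay d | First scan t | True rate 0.38 | True rate 0.65 |
|---|---|---|---|
| 0 | 56 | 0.552 | 0.768 |
| 14 | 70 | 0.476 | 0.719 |
| 28 | 84 | 0.411 | 0.673 |
| 35 | 91 | 0.381 | 0.651 |
| above 35 | after L | up to 1.0 | up to 1.0 |

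Example: 0.38^(56/91.3) = 0.552. With L = 90 the first three values in the 0.38 column are 0.548, 0.471 and 0.405.

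The value 1.0 is a ceiling, because deaths and clinically detected progressions are dated without a scheduled scan. If 10% to 50% of events are dated that way (assumed range), the last row at a true 0.38 becomes 0.94 to 0.69.

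**5. Mixed population.** Suppose 20% of subjects are delayed (assumed; the documents give no figure) and the true rate is 0.38:
- by 28 days: 0.8 × 0.552 + 0.2 × 0.411 = 0.524, a change of −0.028;
- by 42 days: 0.8 × 0.552 + 0.2 × 1.0 = 0.642, a change of up to +0.090.

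**6. Calendar scans under the same model.** A first scan fixed at day 56 gives 0.552 whatever the delays. A calendar scan at day 84 gives 0.411, and one at day 91 gives 0.381.

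**The case against.** The strongest case against is that the harmful direction needs an uncommon pattern: more than about 34 days lost over two consecutive cycle starts. On the 2-week limit, toxicity delays alone cannot produce it. Holds within a cycle need not move the cycle count. Ordinary delays bring the first scan closer to month 3 and so improve ascertainment. The absence of a scan near month 3 in undelayed patients is the larger distortion. All of this stands, and it limits the size of the point. It does not remove it: the documents also contain a 4-week limit and separate non-toxicity interruptions, so the largest displacement is undefined until those passages are reconciled.

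Three stronger readings are tempting, and the documents support none of them.
- A reader might infer that cycle-based scanning can only raise PFS, or always favors the regimen. The table in step 4 shows the opposite for any total delay up to about five weeks.
- A reader might infer that median PFS shifts by the length of the delay. In the same model, if every subject is delayed 28 days, the recorded median falls from 112 to 84 days. Mean recorded PFS rises from about 125 to 136 days, with 68% of records later and 32% earlier.
- A reader might add hidden failures to a null of 0.38 and quote an inflated type I error. That starting point assumes every failure by month 3 is seen in undelayed patients. Under this schedule it is not; the model's undelayed value is 0.552.

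**Conclusion.** The point holds as a design weakness of uncertain direction. Scans are tied to cycle number, the primary endpoint is tied to the calendar, and permitted delays separate the two. For a true rate of 0.38, a delayed patient's chance of being recorded progression-free at 3 months moves from 0.552 down to 0.411 with a 28-day total delay. It can rise toward 1.0 once the total exceeds about 34 days (about 41 with the scan window fully used).

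These sizes rest on exponential PFS, on progression being seen mainly at scans, and on 38% being the true rate. The share of patients delayed this much is not in the documents, so no net bias for the trial can be stated. The scan schedule behind the 38% is not given either, so the bias relative to that benchmark is also unknown. The correction is worth making because it is cheap and removes a dependence of the primary endpoint on tolerability.

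**What to change.** - In Section 7, footnote 6 and in Sections 5.1, 5.2 and 12.1 (and the synopsis), give scan dates in calendar weeks from Cycle 1 Day 1 with a stated window. State that scans are not moved for dose holds, cycle delays or interruptions.
- Choose the calendar so that one scan falls at about week 12-13. An 8-week calendar alone removes the dependence on delay but still leaves no scan between days 56 and 112.
- Define 3 months in days, and say how a scan inside the window is counted. With a 90-day definition, a scan on day 91 would fall after the landmark. A sentence in Section 9.9.3 on late or missed scans belongs with this.
- Reconcile the 2-week limit (Sections 6.2.1 and 6.3.2) with the 4-week limits (Sections 6.1 and 6.4). Which limit applies is a clinical decision outside this review.

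**Cost.** Anchoring the scans is a wording change. The timing of early scans changes, and their number may change, to obtain the week 12-13 scan. In delayed patients some scans will not coincide with a cycle visit.

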8. CORRELATIVE STUDIES AND PROCEDURES

Please see the correlative laboratory manual (CLM) for additional details about the correlatives described below. The analyses described below will be performed upon receipt of funding.

8.1 Peripheral Blood Samples

8.1.1 Plasma for Pharmacokinetics and Pharmacodynamics

In phase 1b, the pharmacokinetics (PK) and pharmacodynamics (PD) of PAC-1 will be assessed following doses administered on Days 1 and 21 of the first cycle. In phase 1b, the PK and PD of entrectinib will be assessed following the dose administered on Days 3 and 21 of the first cycle. Entrectinib will be withheld on Days 1 and 2 to allow assessment of PAC-1 PK when administered as single agent. PAC-1 will be withheld on Days 2 and 3 to allow assessment of entrectinib PK when administered as single agent on Day 3. PKs of both drugs will be assessed on Day 21 to determine effects of repeated dosing or combining of the two drugs. The PK and PD analyses will occur with each dose level.

Administration of PAC-1 on Days 1 and 21 and entrectinib on Days 3 and 21 of Cycle 1 will occur in the morning. Entrectinib administration will occur 1 hour before PAC-1 on Day 21. The dose timing on this day is being specified to accommodate a sampling schedule that minimizes the number of blood draws needed from the patient. Information on the time and number of PAC-1 and entrectinib doses received for the 96 hours prior to the dose on Day 21 will be obtained from subjects. Patients will not receive their PAC-1 dose on Days 2 and 3 of Cycle 1. The doses on these days are being held in order to accurately define the absorption and metabolism of entrectinib when administered as a single agent on Day 3. Likewise, patients will not receive their entrectinib dose on Days 1 and 2 of Cycle 1. The doses on these days are being held in order to accurately define the absorption and metabolism of PAC-1 when administered as a single agent on Day 1. Actual and nominal sample collection times will be recorded on the case report forms and sample tubes.

Sample collections will occur in the mornings on Day 1 (PAC-1 only), Day 3 (entrectinib only), and Day 21 (PAC-1 and entrectinib) of the first cycle.

- Day 1, Cycle 1: Subjects receive only PAC-1.
 - Blood samples are collected immediately prior to oral ingestion of PAC-1 and at the following time points after ingestion: 0.5, 1, 2, 3, 4, 6, 7, and 24 hours.
- Day 3, Cycle 1: Subjects receive only entrectinib.
 - Blood samples are collected immediately prior to oral ingestion of entrectinib and at the following time points after ingestion: 0.5, 1, 2, 3, 4, 6, 7, and 24 hours.
- Day 21, Cycle 1: Subjects receive both PAC-1 and entrectinib.
 - Entrectinib administered 1 hour before PAC-1.
 - Blood samples are collected immediately prior to oral ingestion of entrectinib, 0.5 hour before ingestion of PAC-1, and at the following time points after ingestion of PAC-1: 0.5, 1, 2, 3, 4, 6, 7, and 24 hours. The sample volume is 10-mL at each time point.

8.1.1.1 Pharmacokinetic Analysis

Non-compartment analysis: Non-compartmental analysis of the PAC-1 plasma concentration-time data following doses on Days 1 and 21 for Cycle 1 for each dose level. Also on Days 3 and 21 of Cycle 1, entrectinib plasma concentration data will be performed using WinNonlin 6.3 (Pharsight, St Louis, MO) for subjects in whom complete PK profiles are obtained.

Pharmacokinetic parameters to be estimated following each dose include: 1). area under the PAC-1 plasma concentration-time curve from time 0 to 24 hours (AUC_{0-24}) for days 1 and 21, 2) area under the entrectinib plasma concentration-time curve from 0 to 24 hours (AUC_{0-24}) for Days 3 and 21, 3). area under the PAC-1 plasma concentration-time curves from time 0 to infinity ($AUC_{0-\infty}$) on Day 1 only, 4). area under the entrectinib plasma concentration-time curves from time 0 to infinity ($AUC_{0-\infty}$) on Day 3 only, maximum PAC-1 and entrectinib plasma concentrations (C_{max}), 5). terminal elimination rate constant for both drugs (λ_z), and 6). oral clearance (CL/F) for both drugs.

Statistical Analysis: The influence of multiple dosing (e.g., PAC-1 Day 1 $AUC_{0-\infty}$ vs. Day 21 AUC_{0-24} and entrectinib Day 3 $AUC_{0-\infty}$ vs. Day 21 AUC_{0-24}), concurrent administration of PAC-1 and dose on the pharmacokinetics of entrectinib (e.g., Day 3 $AUC_{0-\infty}$ vs. Day 21 AUC_{0-24}), and concurrent administration of entrectinib and dose on the pharmacokinetics of PAC-1 (e.g., Day 1 $AUC_{0-\infty}$ vs. Day 21 AUC_{0-24}), will be evaluated using a generalized linear models approach. PAC-1 AUC_{0-24} , $AUC_{0-\infty}$, C_{max} and CL/F will be log transformed before statistical analysis. Entrectinib AUC_{0-24} , $AUC_{0-\infty}$, C_{max} and CL/F will be log transformed before statistical analysis. Geometric means will be calculated for the parameters on each study day. The 90% confidence intervals for the geometric mean ratios will be constructed for every comparison.

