5 OVERALL DESIGN AND TREATMENT PLAN

5.1 Phase 1b Dose Escalation Plan

This Phase Ib dose escalation study will evaluate entrectinib in combination with PAC-1 in subjects with metastatic uveal melanoma. Entrectinib will be taken orally on Days 1-28 of each 28 day cycle and PAC-1 will be taken orally on Days 1-21 of each 28-day cycle (see exception for Cycle 1 below), and response to treatment will be evaluated after every 2 cycles. Treatment will continue until disease progression (based on RECIST 1.1 criteria), unacceptable toxicity, subject withdrawal of informed consent, or subject death either from progression of disease, the therapy itself, or from other causes. Subjects who withdrew from study treatment, have progressive disease, or unacceptable toxicities will be followed for survival every 2 months for 12 months from start of study treatment, then every 3 months for up to 24 months.

Pharmacokinetic (PK) and pharmacodynamic (PD) assay for PAC-1 will be performed during Days 1 and 21 of Cycle 1. PAC-1 will be given on Day 1 of Cycle 1, withheld on Day 2 and Day 3 of Cycle 1 then reinitiated on Day 4 of Cycle 1 to continue to Day 21 of the 28-day cycle. For

each successive cycle, PAC-1 therapy will be initiated on Day 1 and continue to Day 21 of the 28-day cycle.

Pharmacokinetic and pharmacodynamic assay for entrectinib will be performed during Days 3 and 21 of Cycle 1. Entrectinib therapy will be withheld on Day 1 and Day 2 of Cycle 1, initiated on Day 3 of Cycle 1 and continue for the remainder of the cycle. For each successive cycle, entrectinib will be initiated on Day 1 and continue for the remainder of the 28 day cycle.

Cycle 1 of Treatment (Cycle = 28 Days)

Drug	Dose	Route	Cycle 1 Frequency
PAC-1	TBD	Orally	Day 1 then Day 4 to Day 21; HELD Day 2 and Day 3
Entrectinib	600 mg		Day 3 to Day 28; HELD Day 1 and Day 2

Cycle 2 and Subsequent (Cycle = 28 Days)

Drug	Dose	Route	Frequency
PAC-1	TBD	Orally	Day 1 to Day 21
Entrectinib	600 mg		Day 1 to Day 28

Study Treatment Dose Levels

Dose Level*	PAC-1 Dose (mg, orally)	Entrectinib (mg, orally)	# of Subjects [^]
-1	625 daily	400 daily	3-6
1 (starting)	625 daily	600 daily	3-6
2	750 daily	600 daily	3-6

*Pharmacokinetics analysis will be performed at both dose levels during Cycle 1.

[^]MTD cohort will be initially expanded to 6 patients, and if no DLT move to Phase 2 study.

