5.3.2 PAC-1

In Phase 1b, PAC-1 (PO) will be dosed at 625 or 750 mg daily in the morning on Days 1-21 of each 28 day cycle (for exception in cycle 1, see below). The dose which is determined to be the MTD will be taken in the morning on Days 1-21 of the cycle in Phase 2.

During Cycle 1 for each dose level, subjects will be instructed to administer their daily dose at the same approximate time (+/- 1 hour) each morning. Subsequent cycles must meet the criteria found in section 6.1. The study drug will be administered in the morning and on an empty stomach with the patient remaining NPO (nothing by mouth), except for water and prescribed medications, for 2 hours before and 1 hour after each dose. Patients will be instructed to take each oral dose of PAC-1 with 8 ounces of water (1 cup, 240 mL).

For Cycle 1, PAC-1 will be given on Day 1 and withheld on Days 2 and 3. The dose on these days are being held in order to determine the PK of single-agent entrectinib on Day 3 of the cycle. PAC-1 treatment will be re-initiated on Day 4 and continue to Day 21 of the 28-day cycle. Administration of PAC-1 on Days 1 and 21 of Cycle 1 will occur in the morning. Information on the time and number of PAC-1 doses received for the 96 hours prior to the dose on Day 21 will be obtained from subjects.

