7: Cycle = 28 days. PAC-1 will be taken once daily, Days 1-21. For Cycle 1, PAC-1 will be given on Day 1 and withheld on Days 2 and 3. The dose on these days is being held in order to determine the PK of single-agent entrectinib on Day 3 of the cycle. PAC-1 treatment will be re-

initiated on Day 4 and continue until Day 21 of the 28 day cycle. Administration of PAC-1 on Days 1 and 21 of Cycle 1 will occur in the morning. Entrectinib will be taken once daily, Days 1-28. Entrectinib therapy will be withheld on Days 1 and 2 and initiated during Cycle 1 on Day 3 to continue until Day 28 of the 28 day cycle. Administration of entrectinib on Days 3 and 21 of Cycle 1 will occur in the morning. Entrectinib administration will occur 1 hour before PAC-1 on Day 21.

8: The PK and PD analyses will occur with each dose level during Phase Ib. Pharmacokinetic and pharmacodynamic sample collections will occur in the mornings on Day 1(PAC-1 only), Day 3 (entrectinib only), and Day 21 (PAC-1 and entrectinib) of the first cycle. Day 1 Cycle 1: Subjects receive only PAC-1. Blood samples are collected immediately prior to oral ingestion of PAC-1 and at the following time points after ingestion: 0.5, 1, 2, 3, 4, 6, 7, and 24 hours. Day 3 Cycle 1: Subjects receive only entrectinib. Blood samples are collected immediately prior to oral ingestion of entrectinib and at the following time points after ingestion: 0.5, 1, 2, 3, 4, 6, 7, and 24 hours. Day 21 Cycle 1: Subjects receive both PAC-1 and entrectinib. Entrectinib will be taken 1 hour before PAC-1. Blood samples are collected immediately prior to oral ingestion of entrectinib, 0.5 hour before ingestion of PAC-1, and at the following time points after ingestion of PAC-1: 0.5, 1, 2, 3, 4, 6, 7, and 24 hours. See Correlative Laboratory Manual (CLM) for additional details regarding these samples.

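### Day 1 PAC-1 AUC0-infinity hangs on one 24 h sample, and the Day 3 pre-dose tube that could support it and test the single-agent premise has no planned PAC-1 assay

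*Combined protocol and SAP*

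**What the plan says.** Section 8.1.1 samples PAC-1 on Day 1 of Cycle 1 before the dose and "at the following time points after ingestion: 0.5, 1, 2, 3, 4, 6, 7, and 24 hours". Section 8.1.1.1 plans "Non-compartmental analysis of the PAC-1 plasma concentration-time data following doses on Days 1 and 21 for Cycle 1 for each dose level". The parameters include the "area under the PAC-1 plasma concentration-time curves from time 0 to infinity" (Day 1 only), the "terminal elimination rate constant for both drugs" and CL/F. No rule says which points enter the terminal fit, and no limit is set on the extrapolated share.

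Section 5.1 has PAC-1 given on Day 1, "withheld on Day 2 and Day 3 of Cycle 1 then reinitiated on Day 4 of Cycle 1". Section 5.3.2 gives the reason: "The dose on these days are being held in order to determine the PK of single-agent entrectinib on Day 3 of the cycle". Entrectinib starts on Day 3. For that day section 8.1.1 states: "Blood samples are collected immediately prior to oral ingestion of entrectinib and at the following time points after ingestion". Calendar footnote 8 assigns the collections as "Day 1(PAC-1 only), Day 3 (entrectinib only), and Day 21 (PAC-1 and entrectinib) of the first cycle". The Day 1 PAC-1 dose and the Day 3 entrectinib dose are both morning doses, and actual sampling times are recorded.

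Section 8.1.1.1 names Day 1 AUC0-infinity against Day 21 AUC0-24 as an example contrast, both for repeated PAC-1 dosing and for adding entrectinib. Every comparison gets a 90% confidence interval for the geometric mean ratio.

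**The concern.** Two things rest on little evidence. First, everything beyond 24 h in AUC0-infinity is extrapolated along a slope set by a pair of samples one hour apart and a single later tube. Oral clearance after a single dose is dose divided by that area, so it carries the same error. Day 1 AUC0-infinity is then the reference in the example PAC-1 contrasts, with 3 to 6 patients per dose level.

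Second, Day 3 is treated as entrectinib alone on the strength of the two-day hold. If PAC-1 is still present, the entrectinib reference already contains some of the exposure whose effect is to be measured, and the interaction ratio would be pulled towards 1. Nothing in the plan would reveal this, although the tube that could is already being drawn.

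**Working it through.** The plan states no PK precision, half-life or extrapolation limit, so there is no figure to reproduce. Sampling times come from section 8.1.1 and footnote 8. Half-life, absorption rate and assay error are assumptions, and half-life is shown as a range.

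**1. Leverage and slope error.** This step depends only on the sampling times. In a log-linear fit with constant log-scale error, leverage is h = 1/n + (t - mean)²/Sxx and SE(slope) = sd/√Sxx.

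- Fit to 6, 7, 24 h: mean 12.33, Sxx = 40.11 + 28.44 + 136.11 = 204.7. Leverage of 24 h = 1/3 + 136.11/204.7 = 0.998.
- Fit to 3, 4, 6, 7, 24 h: mean 8.8, Sxx = 298.8. Leverage of 24 h = 1/5 + 231.04/298.8 = 0.973. Earlier points do not rescue the slope.
- Fit to 6, 7, 24, 48 h: mean 21.25, Sxx = 1158.8. Leverage of 24 h = 0.257 and of 48 h = 0.868.
- Ratio of standard errors = √(1158.8/204.7) = 2.38.

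**2. Extrapolated area and PAC-1 remaining.** Under mono-exponential decline the fraction left at time t is 0.5^(t/half-life). The extrapolated shares below are from a one-compartment oral model (absorption rate 1.5/h).

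| Assumed half-life | Extrapolated beyond 24 h | Extrapolated with a 48 h point | PAC-1 left at the Day 3 dose, 0.5^(48/half-life) |
|---|---|---|---|
| 4 h | 2% | 0% | 0.02% |
| 8 h | 13% | 2% | 1.6% |
| 12 h | 26% | 7% | 6.3% |
| 24 h | 51% | 26% | 25% |
| 36 h | 64% | 40% | 40% |

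**3. Effect on estimated AUC0-infinity.** Simulated non-compartmental analysis: one compartment, absorption rate 1/h, 15% log-normal error per sample, linear-up/log-down area, slope from the last three points (6, 7, 24 h without the extra tube; 7, 24, 48 h with it). Entries are the 5-95% range of estimated over true.

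| Assumed half-life | One patient, to 24 h | One patient, with 48 h | Geometric mean of 9, to 24 h | Geometric mean of 9, with 48 h |
|---|---|---|---|---|
| 6 h | 0.90-1.12 | 0.90-1.11 | 0.97-1.04 | 0.97-1.04 |
| 12 h | 0.85-1.25 | 0.90-1.12 | 0.95-1.09 | 0.97-1.04 |
| 24 h | 0.72-2.05 | 0.87-1.21 | 0.93-1.38 | 0.96-1.08 |

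Separate runs of this simulation move the range limits by 0.01 to 0.02. With 20% error and absorption rate 1.5/h, the single-patient range at 24 h goes from 0.67-2.96 to 0.84-1.33.

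**4. Two-phase decline.** With a 3 h fast phase (weight 0.7) and a 24 h terminal half-life, the error-free ratio of estimated to true AUC0-infinity is 0.83 from the planned samples and 0.97 with the 48 h point. The planned design can therefore be biased as well as imprecise.

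**The case against.** The strongest reply is that the half-life is wholly assumed. The protocol reports 44 patients already given PAC-1 and refers to the Investigator's Brochure, so a half-life that justifies the schedule may exist in a source not available here. At about 6 h the tail beyond 24 h is small, the 48 h level is 0.5^(48/6) = 0.4% of the mono-exponential starting level and may be unquantifiable, and the slope gains nothing. This stands, and it makes the precision argument conditional. It does not dispose of the second use of the tube: a result below the assay limit would support the single-agent premise down to that limit.

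A reader might infer that slope error dominates the planned ratios. The group-level figures do not support that at 12 h or below, where the effect is a few percent; it becomes large only towards 24 h. A reader might also infer that all PAC-1 comparisons are affected. Section 8.1.1.1 gives the AUC0-infinity contrasts as examples, and AUC0-24 and Cmax, also to be analysed, need no extrapolation. Nor do the documents show that PAC-1 is present on Day 3, only that nobody plans to look. Sample details are deferred to a laboratory manual that was not available, so the statement is that the protocol plans no such assay, not that none will be run.

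It is tempting to use the Day 4 morning sample too, nominally 72 h after PAC-1. That sample follows the first entrectinib dose. Section 5.6.2 reports in vitro potential for entrectinib to inhibit or induce CYP enzymes, and the documents do not give PAC-1's metabolic route. It could bring entrectinib exposure into the PAC-1-alone reference.

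Finally, these are exploratory endpoints, analysed only once funding is received. That is true and limits the priority.

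**Conclusion.** The point holds as a cheap improvement, not as an error that threatens the trial. On the sampling times alone, the Day 1 PAC-1 slope depends almost entirely on the 24 h tube, and a quantifiable 48 h value would cut its standard error about 2.4-fold, assuming log-linear decline and constant log-scale error. It would not settle the slope in all cases: at a 36 h half-life 40% of the area would still be extrapolated. The effect on group results is negligible at a half-life of about 6 h, a few percent at 12 h and substantial at 24 h; the documents do not say which applies. Separately, the single-agent label for Day 3 is an unchecked premise that the same tube can test. The consequences are confined to the Phase 1b comparisons that use AUC0-infinity or the clearance derived from it, and to the entrectinib-alone reference. AUC0-24 and Cmax for PAC-1, the MTD and the Phase 2 primary endpoint are untouched.

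**What to change.** In section 8.1.1, section 8.1.1.1 and calendar footnote 8, state that the Day 3 pre-dose tube is assayed for PAC-1 as well as entrectinib. Then:

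- If PAC-1 is quantifiable, include the value in the Day 1 terminal slope and AUC0-infinity at its recorded actual time, since 48 h is only nominal.
- Report the Day 3 pre-dose PAC-1 level, or the assay limit it falls below, as the check on the single-agent premise.
- Report the extrapolated share with each AUC0-infinity.
- State that the Day 4 sample is not used in the PAC-1-alone estimates, because it follows entrectinib.

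The cost is one extra PAC-1 assay per Phase 1b patient, about 9 to 12 in all given the enrolment range in section 12.3.1, on blood already drawn. There is no new visit, blood draw or dose change. If the laboratory manual already provides for this assay, only the protocol text needs to be aligned.
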